3.3 Study Design

This is a double-blind, placebo controlled study of VentaProst (Active) as compared to placebo (Control). Active is inhaled epoprostenol administered via the VentaProst delivery system in 10 COVID-19 positive patients. Control is inhaled 0.9% sodium chloride solution administered via the VentaProst delivery system in 10 COVID-19 positive patients. Throughout the remainder of the protocol both Active and Control will be referred to as "study drug". This study will evaluate the potential therapeutic benefit of VentaProst in treating patients with COVID-19 who require mechanical ventilation and are at risk for the progression of respiratory and/ or cardiac/circulatory failure. This study will assess the efficacy and safety of VentaProst at an initial dose of 13.6 ng/kg/min (A range from 3.4-30.6 ng/kg/min may be administered as clinically required for a maximum of 10 days at the discretion of the Investigator. Patients will be followed through Day 28 to assess clinical outcomes.

Patients will be consented and randomized to either the Active or Control group within 48 hours of being placed on mechanical ventilation. Informed consent may be obtained after some screening study procedures were collected as part of the patient's standard of care treatment. Patients will be administered study drug using the VentaProst delivery system which allows up and down titration of study drug to achieve hemodynamic and oxygenation stability. The starting dose of study drug will be initiated at 13.6 ng/kg/min. Based on hemodynamic and oxygenation parameters, the dose of study drug can be increased in 3.4 ng/kg/min increments up to a maximum of 30.6 ng/kg/min or down to a minimum of 3.4 ng/kg/min.

All study staff with the exception of the unblinded pharmacist and Sponsor CRA will be blinded to which treatment regimen a patient has been assigned. Titration and weaning will be performed the same for all patients. Study drug will be administered based on the pump rate calculated for active treatment in mL/hr. Titration guidelines are provided in Section 5.3.3 and Table 3.

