6.2 Secondary Endpoints

- 1. Improvement in oxygenation defined as any one of the following:
 - Stabilization of PaO2/FIO2 >250
 - Improvement in FIO2 by 50% or improvements ≥15% in S/F, P/F ratio from baseline at 12 hours, Day 5 and Day 10 (or end of treatment)
- 2. Improved clinical outcomes defined as one of more of the following:
 - Time to extubation following the site's extubation protocol

- Free from re-intubation
- Reduction in ICU days
- Reduction in the number of re-admissions to the ICU due to COVID-19 within 28 days
- Reduction in total hospital days
- Mortality [28 days] defined as Cardiopulmonary mortality from all causes

3. Safety and tolerability

 Monitoring of adverse events (AEs), serious adverse events (SAEs), chest CT or Chest X-rays, vital signs, ventilatory/oxygenation parameters, and laboratory tests.

6.3 Exploratory endpoints will include (where available as part of standard of care):

- Change in LDH
- Change in fibrinogen
- Change in WBC count including lymphocytes and neutrophil subsets
- Change in triglycerides
- Change in ferritin
- Change in CRP / ESR
- Change in IL-6
- Change in D-Dimer

Changes in these parameters will be assessed for each patient from baseline to end of study as well as changes between the active and control groups.

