9.1.3 Day 28/End of Study (EOS)

- Assess AEs/SAEs
- Assess Mortality
- Assess concomitant medications

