10.3 Analyses Sets

All patients who are enrolled in the study and who receive at least one dose of study drug will be included in the intent-to-treat (ITT) analyses of pharmacodynamic and safety data. All available data will be used and missing data will not be estimated or carried forward in any statistical summary or analyses.

Descriptive summary statistics include the number of patients, mean, median, percent coefficient of variation (% CV) (if required), standard deviation, and minimum and maximum values (quantitative variables) or the number of patients and percentages by category (qualitative variables). Changes will be assessed as the difference between baseline measurements and the appropriate post-dose measurements unless otherwise specified. Mean differences between active and control groups (when available) will be assessed and significance will be determined on the basis of a 95% CI. Individual patient listings of data will also be provided to allow for review of all pharmacodynamic, safety, and tolerability parameters.

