10.6.2 Secondary Efficacy Endpoints

Key secondary endpoints include:

- 1. Improvement in oxygenation defined as any one of the following:
 - Stabilization of PaO2/FIO2 >250
 - Improvement in FIO2 by 50% or improvements ≥15% in S/F, P/F ratio from baseline at 12 hours, Day 5 and Day 10 (or end of treatment)
- 2. Improved clinical outcomes defined as one of more of the following:
 - Time to extubation following the site's extubation protocol
 - Free from reintubation
 - Reduction in ICU days
 - Reduction in the number of re-admissions to the ICU due to COVID-19 within 28 days
 - Reduction in total hospital days
 - Mortality [28 days] defined as Cardiopulmonary mortality from all causes
- 3. Safety
 - Monitoring of adverse events (AEs), serious adverse events (SAEs), chest CT or Chest X-rays, vital signs, ventilatory/oxygenation parameters, and laboratory tests.

10.6.3 Key Exploratory Endpoints include:

- Change in LDH
- Change in fibrinogen
- Change in WBC count including lymphocytes and neutrophil subsets
- Change in triglycerides
- Change in ferritin
- Change in CRP / ESR
- Change in IL-6
- Change in D-Dimer

Changes in these parameters will be assessed for each patient from baseline to end of study as well as changes between the active and control groups.

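### Time to extubation is averaged only over patients extubated by Day 28, which shrinks a real benefit and can erase or reverse it; ICU days and hospital days have no stated horizon

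*Combined protocol and SAP*

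**What the plan says.** The references are to the current, placebo-controlled version of the protocol.

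- **Endpoints.** Three secondary clinical items are durations: "Time to extubation following the site's extubation protocol" (Section 10.6.2), "Reduction in ICU days" (Section 6.2) and "Reduction in total hospital days" (Section 10.6.2). None has a time limit, a censoring rule or a value for a patient who has not reached the event.
- **Follow-up.** Section 3.3: "Patients will be followed through Day 28 to assess clinical outcomes".
- **Analysis.** Section 10.3: "Mean differences between active and control groups (when available) will be assessed and significance will be determined on the basis of a 95% CI". Its summaries for quantitative variables are simple ones ("Descriptive summary statistics include the number of patients, mean, median" and measures of spread), with no time-to-event summary.
- **Missing values.** Section 10.3: "All available data will be used and missing data will not be estimated or carried forward in any statistical summary or analyses". The synopsis repeats this rule.
- **No further plan.** Section 10.1 says that no statistical analysis plan will be developed.
- **Day 28 data.** Section 9.1.3 lists adverse events, "Assess Mortality" and concomitant medications. Ventilation, ICU and hospital status are not listed, and ventilator parameters in Table 2 stop at Day 10.
- **Related text.** The synopsis row on efficacy analysis adds a summary of success or failure on the endpoints. Section 10.6.1 counts a patient not extubated by Day 10 as a failure on the primary endpoint.

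**The concern.** A patient still on the ventilator at Day 28 has no extubation time, and Section 10.3 allows none to be supplied. The mean time to extubation is then the mean among patients already extubated. That group is selected by the outcome, and the drug can change who is in it. A patient moved by treatment from not extubated by Day 28 to extubated on Day 20 adds a long value to the Active mean and makes that arm look worse. The information that the remaining patients took more than 28 days is discarded.

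For ICU days and hospital days the fault is different. The plan sets no horizon, so an unfinished stay could be dropped, with the same bias, or counted up to Day 28, without it.

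At stake are the direction and size of effect on secondary clinical outcomes, which is most of what a trial of about 20 patients can offer. Section 10.3 also attaches a significance statement to these mean differences.

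**Working it through.** **Inputs from the documents.** About 20 patients, randomised 1:1, so 10 per arm (Sections 3.3, 4 and 10.4); follow-up to Day 28; difference in means with a 95% CI on available data. The plan states no power, effect size or extubation rate, so there is no planned figure to reproduce.

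**Assumptions.** Every rate below is assumed, and all patients are taken to be alive at Day 28. The comparison is between (a) the mean among patients extubated before Day 28 and (b) the mean with every patient counted to Day 28, those not extubated contributing 28 days (the restricted mean).

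**1. Hand example, 10 per arm.** Control: five extubated on days 6, 8, 10, 12, 14; five still ventilated. Active: the same five times, three more on days 20, 23, 26; two still ventilated.

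- (a) Control 50/5 = 10.0; Active 119/8 = 14.9. Difference +4.9 days, an apparent harm.
- (b) Control (50 + 5×28)/10 = 19.0; Active (119 + 2×28)/10 = 17.5. Difference −1.5 days, a benefit.

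**2. Uniform speed-up (constant hazard λ).** Available mean = 1/λ − 28e^(−28λ)/(1 − e^(−28λ)). Restricted mean = (1 − e^(−28λ))/λ.

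Control median 20 days, hazard ratio 2: λ = ln 2/20 and ln 2/10; still ventilated at Day 28, 0.3789 and 0.1436.

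- (a) 28.85 − 28×0.3789/0.6211 = 11.77; 14.43 − 28×0.1436/0.8564 = 9.73. Difference −2.04.
- (b) 28.85×0.6211 = 17.92; 14.43×0.8564 = 12.36. Difference −5.56.
- Share retained: 2.04/5.56 = 0.37.

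| Control median (days) | Control still ventilated at Day 28 | Hazard ratio | (a) Available | (b) Restricted | Retained |
|---|---|---|---|---|---|
| 10 | 14% | 1.5 | −1.73 | −3.26 | 53% |
| 10 | 14% | 2.0 | −3.11 | −5.29 | 59% |
| 14 | 25% | 1.5 | −1.40 | −3.37 | 42% |
| 14 | 25% | 2.0 | −2.63 | −5.68 | 46% |
| 20 | 38% | 1.5 | −1.05 | −3.17 | 33% |
| 20 | 38% | 2.0 | −2.04 | −5.56 | 37% |
| 28 | 50% | 1.5 | −0.78 | −2.79 | 28% |
| 28 | 50% | 2.0 | −1.53 | −5.05 | 30% |

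The effect shrinks but does not reverse in expectation.

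**3. Benefit confined to slow patients.** Exponential times: 60% of patients with mean 8 days in both arms, 40% with mean 60 days in Control and 20 in Active.

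- Still ventilated at Day 28: 0.6e^(−28/8) + 0.4e^(−28/60) = 26.9% Control; 0.6e^(−28/8) + 0.4e^(−28/20) = 11.7% Active.
- (b) 13.6 against 10.7 days.
- (a) (13.605 − 28×0.2690)/0.7310 = 8.3 against (10.682 − 28×0.1168)/0.8832 = 8.4. The benefit disappears.

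**4. Non-extubations turned into late extubations.** A share p is extubated at mean day 10 in both arms. The rest of Control is still ventilated at Day 28; in Active a fraction q of the rest is extubated at about day 22.

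- (a) difference = [10p + 22(1 − p)q]/[p + (1 − p)q] − 10.
- (b) difference = −6(1 − p)q.
- With p = q = 0.5: 10.5/0.75 − 10 = +4.0 against −1.5.
- Over p = 0.4, 0.5, 0.6 and q = 0.25, 0.5, 0.75: (a) +1.7 to +6.4, (b) −0.6 to −2.7. The sign reverses in all nine settings.

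**5. Simulated trials of 10 per arm (4,000 per pattern).**

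| | Median 20, hazard ratio 2 | Pattern 4, p = q = 0.5 |
|---|---|---|
| Wrong sign, available data | 32% | 91% |
| Wrong sign, all counted to Day 28 | 10% | 34% |
| Significant benefit, available data | 7% | 0.1% |
| Significant benefit, log-rank censored at Day 28 | 27% | 12% |

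**6. Precision.** With all 10 per arm, the 95% CI half-width is 2.101×√(2/10) = 0.94 SD. With the 5 and 8 patients left in step 1 it is 2.201×√(1/5 + 1/8) = 1.25 SD.

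**The case against.** The strongest case is that the plan never says a patient with an unfinished duration is excluded. Section 10.3 takes every dosed patient into the analyses, and days in ICU or hospital up to Day 28 are observed; counting them estimates nothing. A reader might infer that all three durations lose these patients. The documents support that only for time to extubation; for the other two, the horizon is undefined.

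Second, the synopsis also summarises success or failure on the endpoints, and a still-ventilated patient could simply be a non-success who stays in the denominator. But the synopsis defines no per-patient success for a duration, and the mean comparison in Section 10.3 stands beside it. The ambiguity remains.

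Third, reversal comes from chosen patterns. A reader might infer that the analysis would be expected to turn a benefit into a harm. That is not supported: a uniform benefit is attenuated, and reversal in expectation needs a drug that mainly converts non-extubations into late ones.

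Fourth, these are secondary items in an exploratory trial with no sample-size calculation. The primary endpoint is not affected by this route, and patient numbers and listings would show unequal denominators. This limits the consequence, but visible denominators do not correct a biased mean.

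**Conclusion.** The point holds for time to extubation. The stated method compares means in a subset selected by the outcome, and no other document is planned that could correct it. Under constant hazard, with 14% to 50% of controls still ventilated at Day 28 and hazard ratios of 1.5 to 2, 28% to 59% of the true difference survives. Where benefit falls on slow patients, it can be erased (8.3 against 8.4 days, when the restricted means are 13.6 and 10.7) or reversed (+1.7 to +6.4 days, when the true differences are −0.6 to −2.7).

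For ICU days and hospital days the conclusion is narrower: the plan must say whether unfinished stays are dropped or counted to Day 28.

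The sizes rest on assumed rates and on no deaths. Section 2.1 cites mortality of 22% to 62% in the critically ill, so any replacement must also say how deaths count. The change should be made, but the affected endpoints are secondary.

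**What to change.** In Sections 6.2, 10.3 and 10.6.2, replace the mean comparison for these three items:

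- Analyse time from randomisation to extubation, to ICU discharge and to hospital discharge as time-to-event through Day 28, in all randomised and dosed patients.
- Censor event-free survivors at Day 28.
- Treat death before the event as a competing event, neither censored nor excluded.
- Report cumulative incidence by arm.

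An alternative is to rank all patients on days to Day 28, giving 28 to those still ventilated, in ICU or in hospital and the worst rank to deaths. Scoring survivors only would bring back selection after randomisation.

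Add to Section 9.1.3 and Table 2 the dates of extubation, ICU discharge and hospital discharge, and ventilation, ICU and hospital status at Day 28, taken from the chart.

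The cost is a few sentences, standard code and a few chart fields. A curve or rank summary replaces a simple mean. Clinical management does not change.

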10.4 Randomization

Patients will be randomized 1:1. A randomization schedule will be provided to the unblinded pharmacist. Should unblinding be requested due to a medical emergency, the unblinded pharmacist will work with the medical monitor or Sponsor unblinded CRA to obtain the required information.

10.5 Demographic and Other Baseline Characteristics

Continuous demographic and other baseline characteristics (such as age, weight, and height) will be summarized using n, mean, SD, median, minimum, and maximum. Qualitative characteristics (such as gender and race) will be summarized by counts and percentages.

10.6 Criteria for Evaluation

10.6.1 Primary Efficacy Endpoint

The primary efficacy endpoint:

- 1. Reduction of respiratory failure. Failure is defined by any one of the following:
 - Requires VV ECMO
 - Inability to extubate patient within 10 days or reintubation within <24 hours
 - Change in S/F, oxygenation index and P/F ratio (\geq 15%) from baseline to 12 hours, Days 1, 2, 3, 4, 5, 6, 7, 8, 9 and Day 10 (or end of treatment)

or

- 2. Reduction of cardiac or circulatory failure. Failure is defined by any one of the following:
 - Need to begin inotropic therapy or 10% increase in current vasopressor therapy

- Worsening hemodynamic parameters
- Cardiac troponin >20 % from baseline
- BNP \geq 15% of baseline
- Need for temporary mechanical circulatory support (IABP, Impella)
- Requires VA ECMO

10.6.2 Secondary Efficacy Endpoints

Key secondary endpoints include:

- 1. Improvement in oxygenation defined as any one of the following:
 - Stabilization of PaO2/FIO2 >250
 - Improvement in FIO2 by 50% or improvements ≥15% in S/F, P/F ratio from baseline at 12 hours, Day 5 and Day 10 (or end of treatment)
- 2. Improved clinical outcomes defined as one of more of the following:
 - Time to extubation following the site's extubation protocol
 - Free from reintubation
 - Reduction in ICU days
 - Reduction in the number of re-admissions to the ICU due to COVID-19 within 28 days
 - Reduction in total hospital days
 - Mortality [28 days] defined as Cardiopulmonary mortality from all causes
- 3. Safety
 - Monitoring of adverse events (AEs), serious adverse events (SAEs), chest CT or Chest X-rays, vital signs, ventilatory/oxygenation parameters, and laboratory tests.

10.6.3 Key Exploratory Endpoints include:

- Change in LDH
- Change in fibrinogen
- Change in WBC count including lymphocytes and neutrophil subsets
- Change in triglycerides
- Change in ferritin
- Change in CRP / ESR
- Change in IL-6
- Change in D-Dimer

Changes in these parameters will be assessed for each patient from baseline to end of study as well as changes between the active and control groups.

10.7 Extent of Exposure

Exposure data will be summarized by using frequencies and percentages.

10.8 Safety Analyses

Safety measurements include AE/SAEs, vital signs, chest assessments (Chest CT or Chest X-ray), laboratory tests, and oxygenation/ventilatory parameters. Safety data will be summarized by using frequencies and incidence rates.

10.8.1 Adverse Events

AEs will be classified into standardized medical terminology from the verbatim description (Investigator term) using the Medical Dictionary for Regulatory Activities (MedDRA). AEs will be presented by preferred term nested within System Organ Class. Verbatim description and all MedDRA level terms, including the lower level terms, for all AEs will be contained in the data listings of the clinical study report (CSR).

AEs will be summarized by presenting the incidence of AEs. Although a MedDRA term may be reported more than once for a patient, that patient will be counted only one time in the incidence count for that MedDRA term.

Treatment-emergent adverse events (TEAEs) will be analyzed. AEs that are not treatment-emergent will be listed. A TEAE is defined as

- AEs that emerge during treatment, having been absent at pretreatment, or
- Reemerge during treatment, having been present at pretreatment but stopped prior to treatment, or
- Worsen in severity or frequency during treatment relative to the pretreatment state, when the AE is continuous.

Adverse events of special interest (AESI) will be analyzed. An AESI is defined as:

- Serious or non-serious adverse that is one of scientific and medical concern specific to the sponsor's product for which ongoing monitoring and rapid communication by the investigator to the sponsor is required
- Events or symptoms thought to potentially be associated with the investigational compound, device, or disease under study, or
- Can arise with any use of a drug/device (e.g. off-label use, use in combination with another approved drug), with any route of administration, formulation, or dose, including an overdose.

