5.2 Treatments Administered

Patients will receive study drug via mechanical ventilator, starting at 13.6 ng/kg/min. If determined by the treating physician, study drug can be up titrated in 3.4 ng/kg/min increments to a maximum of 30.6 ng/kg/min or down to a minimum of 3.4 ng/kg/min. At the Investigator's discretion, the patient will be weaned off the drug in 3.4 ng/kg/min increments. Study drug will be administered based on the pump rate calculated for the active treatment but delivered in mL/hr. Study drug can be administered up to 10 days.

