5.3.4 Study Medication Weaning

Patients will be weaned from study drug slowly to avoid rebound vasoconstriction. During weaning, doses will be decreased in steps of 6.8 ng/kg/min increments, with a no less than 5 minutes between changes as clinically indicated. The weaning process should occur in isolation to other treatment changes (no changes in inotropes, vasopressors, or vasodilators) whenever possible. Patients will be observed closely before, during, and after dose changes. In the event patients demonstrate signs of hemodynamic instability or a decrease in oxygenation indicated by pulse oximetry during downward titration, the dose will be returned to its previous level. Once patients have been stable for at least 15 minutes, repeat attempts at dose reduction may be undertaken. The process will continue until patients are fully weaned. Patients will be monitored for safety and efficacy throughout study drug administration.

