7.2 Adverse Events

7.2.1 Definitions

Adverse events are any untoward medical occurrence in a patient administered a pharmaceutical product and which does not necessarily have to have a causal relationship

with this treatment. For the purposes of this study, this will include unanticipated medical events in the judgment of the investigator. *A pre-existing condition* or symptom is one that is present at the start of the study and is reported as part of the patient's medical history. A pre-existing condition or symptom should be reported as an AE only if its frequency, intensity or character worsens during study treatment.

All AEs that occur from the time of the first dose of study medication through the End of Study (Day 28) will be recorded and reported as Treatment-Emergent Adverse Events (TEAE). All AEs must be appropriately documented in the patient's medical chart/source documentation and on the DCFs. When known, investigators should report syndromes rather than list symptoms associated with the syndrome.

All AEs that are ongoing at the conclusion of the study should be followed until: a) resolution/stable sequelae; b) the Investigator determines that it is no longer clinically significant; or, c) the study patient is lost to follow-up. If no follow-up is provided, the Investigator must provide a written justification.

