7.2.2 Adverse Events of Special Interest (AESI)

Pulmonary edema and pulmonary hemorrhage are AEs of special interest due to the mode of action of epoprostenol. If an AE of special interest occurs, the Sponsor will be notified of this occurrence within 24 hours.

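### Sections 7.2.1 and 10.8.1 define treatment-emergent AEs differently; read literally, 10.8.1 moves AEs with onset after the last dose from the TEAE analysis to listings

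*Combined protocol and SAP*

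**What the plan says.** References are to the last protocol version in the combined document.

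- **Section 7.2.1 (Definitions)** sets a calendar window, running "from the time of the first dose of study medication through the End of Study (Day 28"), and classes every AE in that window as a TEAE.
- **Section 10.8.1 (Adverse Events)** says that TEAEs are the events to be analysed and that "AEs that are not treatment-emergent will be listed". It then defines a TEAE in three parts. The first is "AEs that emerge during treatment, having been absent at pretreatment". The other two cover events that come back, or get worse, while the patient is on treatment. It gives no day count, no post-dose window and no reference to 7.2.1.
- **Section 5.2** limits exposure: "Study drug can be administered up to 10 days". Section 3.4 lists the treatment period and the 28-day follow-up as separate items.
- **Section 10.1** states that no statistical analysis plan will be developed.
- **Section 7.2.2** names the AEs of special interest (AESIs): "Pulmonary edema and pulmonary hemorrhage are AEs of special interest due to the mode of action of epoprostenol". Section 10.8.1 gives a general AESI definition that also takes in events potentially associated with the disease under study.

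**The concern.** An AE that begins after the last dose and by Day 28 is a TEAE under 7.2.1. Under a literal 10.8.1 it is not, and it appears only in a listing. With no separate SAP, whoever programs the tables must choose between the rules, possibly after seeing the data.

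The choice matters because safety is a stated endpoint, and the synopsis says it is summarised for both groups by frequencies and incidence rates. Under a literal 10.8.1 the counting window has no fixed length. It closes when drug stops, and several provisions link stopping to the patient's course:

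- Section 4.4.1 allows removal for hypotension, rising vasopressor need, worsening oxygenation, massive hemoptysis or pulmonary edema.
- Section 5.4.2 requires a positive-pressure ventilation mode for delivery, so extubation ends exposure.
- Section 9.1.2.1 leaves duration to the investigator.

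Patients who improve and patients who deteriorate can both have short windows. If the drug affects either course, average window length can differ between arms, and crude incidence over unequal windows is then not a like-for-like comparison. With about 10 patients per arm, one or two reclassified patients change the table.

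**Working it through.** The plan states no figure on this point, so there is none to reproduce. The check is window arithmetic.

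**Inputs**

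- Maximum treatment, T = 10 days (Sections 3.4 and 5.2).
- End of AE follow-up, F = Day 28 (Section 7.2.1), with a visit window of plus or minus 2 days (Table 2).
- Shorter treatment of 5 days or 1 day: assumed scenarios, since the protocol allows earlier stopping but gives no expected duration.

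**Formula:** share of follow-up outside the TEAE window = (F − T) / F.

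| Rule | T | F | Days outside | Share |
|---|---|---|---|---|
| 7.2.1 | any | 28 | 0 | 0% |
| 10.8.1, literal | 10 | 28 | 28 − 10 = 18 | 64.3% |
| 10.8.1, literal | 5 (assumed) | 28 | 28 − 5 = 23 | 82.1% |
| 10.8.1, literal | 1 (assumed) | 28 | 28 − 1 = 27 | 96.4% |
| 10.8.1, literal | 10 | 26 | 26 − 10 = 16 | 61.5% |
| 10.8.1, literal | 10 | 30 | 30 − 10 = 20 | 66.7% |

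These are shares of calendar days. Turning them into events needs an assumption that the documents do not supply.

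**Illustration only.** Assume a constant hazard over 28 days and 10 patients per arm. If the 28-day incidence is p, the incidence in the first 10 days is 1 − (1 − p)^(10/28).

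| p over 28 days | Incidence in first 10 days | Patients per arm, 28 days | Patients per arm, 10 days |
|---|---|---|---|
| 30% | 12.0% | 3 | 1.2 |
| 50% | 21.9% | 5 | 2.2 |
| 80% | 43.7% | 8 | 4.4 |

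If risk is concentrated in the first days of ventilation, fewer events move than this.

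**Does 10.8.1 really mean something narrower than 7.2.1?** Two features suggest so. Section 3.4 separates treatment from follow-up. Also, Table 2 starts AE monitoring at Baseline 0 Hr, so under 7.2.1 nearly every recorded AE is a TEAE and the listing-only category in 10.8.1 would be almost empty. Neither feature settles which section prevails.

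**The case against.** The strongest reply is that the two sections can be read together. The three parts of the 10.8.1 definition classify an AE by its pretreatment status, while 7.2.1 supplies the only explicit window. On that reading no TEAE is displaced. The reading is possible, and nothing in the documents rules it out. But the words on treatment period in 10.8.1 do not say it, and no SAP will.

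A reader might infer four stronger things that the documents do not support:

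- **That the analysis certainly discards most of follow-up.** No section gives 10.8.1 precedence. Even read literally, later AEs are still collected and listed, SAEs run to Day 28 (Sections 7.2.7 and 7.2.8), and 28-day mortality is a separate endpoint. The sentence in 10.8.1 on AE incidence is not expressly confined to TEAEs, and the AESI analysis there has no on-treatment limit.
- **That 64% of events are displaced.** The figure is a share of days.
- **That rebound events are lost.** Section 5.3.4 says "Patients will be weaned from study drug slowly to avoid rebound vasoconstriction", which concerns stepwise reduction while drug is still running. Such events fall on treatment under both rules. Only onset after the final step would differ.
- **That 10.8.1 replaces the two named AESIs.** It does not say so. The specific list and the general definition can coexist, though the general one is loose enough to dilute the two named risks.

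It is also fair to say that an on-treatment table is defensible for a drug with a half-life generally under 3 minutes after an IV bolus (Section 2.2.3), and that counting to Day 28 adds events from the underlying critical illness. That supports keeping such a table beside the fixed-window one. It does not support leaving two definitions in force.

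**Conclusion.** The contradiction is real and should be corrected before analysis. If 10.8.1 is applied literally, AEs with onset in at least 18 of 28 calendar days (64%; 61.5% to 66.7% across the end-visit window) move from the TEAE analysis to listings, and each patient's counting window depends on when and why drug stopped. If 7.2.1 is applied, nothing moves. The size therefore rests on which section governs, which the documents leave open, and on treatment lasting the full 10 days; earlier stopping raises the share. How many events would change category cannot be stated from the documents. The AESI wording is a secondary point with no figure attached.

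**What to change.** In Section 10.8.1:

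1. Define a TEAE as an AE that starts or worsens from first dose of study drug through Day 28, matching 7.2.1.
2. Tabulate TEAEs by arm over that fixed window, and add an on-treatment table as supportive.
3. State that the AESI table reports the two events named in 7.2.2.

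The cost is a few sentences and one extra table. AEs are already collected to Day 28, so no assessment or data field is added. The small downside is that later events from the underlying critical illness also enter the main table; the on-treatment table offsets this. The SAE window in 7.2.7, which starts at randomization, can stay as it is, provided the table footnotes state the different starting points.
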